15.8.1 Evaluation of AEs

Below is the list of the safety endpoints in the trial:

Primary endpoint	At least one TEAE
Secondary endpoint	At least one solicited TEAE
Secondary endpoint	At least one IMP-related AE
Secondary endpoint	At least one treatment-emergent serious adverse events (SAE)
Other	At least one treatment-emergent systemic allergic reaction including anaphylaxis
Other	At least one TEAE treated with adrenaline/epinephrine
Other	At least one treatment-emergent severe local swelling or oedema of the mouth and/or throat
Other	A TEAE of eosinophilic oesophagitis
Other	A TEAE leading to discontinuation
Other	Daily duration of recurrent TEAEs

The different types of AEs (TEAEs, solicited TEAEs, IMP-related AEs, treatment-emergent SAEs, treatment-emergent systemic allergic reactions including anaphylaxis, TEAEs treated with adrenaline/epinephrine, treatment-emergent severe local swellings or oedemas of the mouth and/or throat, TEAEs of eosinophilic oesophagitis, and TEAE leading to discontinuation) in the above table will be summarised by system organ class (SOC) and preferred term (PT).

Summaries will include number and proportion of subjects having the event, as well as number of events. For the proportion of subjects with at least one events the exact 95% confidence interval will also be presented.

The different types of AEs mentioned in the above table will generally also be summarised according to severity, relationship to trial product, outcome, action taken, seriousness, and number of events leading to treatment discontinuation. However, in case of few events of the specific type, these details will be listed instead.

Duration of recurrent TEAEs will be summarised according to PT.

Most frequent AEs defined as those occurring in more than 2% of subjects will be summarised according to SOC and PT. Duration of most frequent AEs, as well as time to onset of most frequent AEs, will be summarised according to SOC and PT.

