1.3 Trial rationale

Currently, the HDM SLIT-tablet is approved for use in the adolescent population in some major regions of the world, but still lacking in some e.g. North America. Subpopulation results from the completed phase III trials (adults/adolescents) showed that treatment with the HDM SLIT-tablet in subjects with HDM AR/C with or without asthma was well tolerated and efficacious.

The purpose of this trial is to supplement the safety database supporting an application to extend the indication into the adolescent population in markets where the HDM SLIT-tablet is currently only approved for adult patients.

Endpoints have been selected based on safety data obtained in previous trials with the HDM SLIT-tablet. Safety endpoints listed will support the primary objective to evaluate the overall safety and tolerability of the HDM SLIT-tablet in the adolescent population.

Subjects will be enrolled to receive treatment with the HDM SLIT-tablet (12 SQ-HDM) for a period of 28 days. A treatment period of 28 days is chosen based on previous experience with the onset of AEs being mainly within the first few weeks of treatment with the HDM SLIT-tablet.

The primary safety objective will be assessed based on collection of adverse events related to the 28-day treatment period. The secondary endpoints are focused on the characterisation of the frequency of pre-specified particular AEs expected to occur with the local application of the HDM SLIT-tablet (solicited AEs).

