15.1 Sample size and power considerations

Approximately 250 subjects will be included in the study.

The study will supplement the safety database supporting an application for extension of the indication into the adolescent population in markets where the HDM SLIT-tablet is currently only approved for use in adults. Therefore, the number of subjects has been chosen so that in total, at the time of submission, approximately 500 adolescent subjects have been exposed to the HDM SLIT-tablet (12 SQ-HDM dose) in clinical trials.

The rationale for doing this, is to be able to exclude a 1% or higher proportion of subjects experiencing an AE for rare events, when the observed proportion is 0.2%. The argumentation is as follows: no events of severe systemic allergic reactions or severe local swellings have been reported in the 265 adolescent subjects exposed to 12 SQ-HDM in clinical trials, indicating that the risk in adolescents is no higher than that observed in adults. If 1 event were to occur in this study, it will correspond to an overall proportion of 0.2%, and the upper limit of the two-sided 90% confidence interval for the proportion will then be 0.95%, i.e. it can be concluded that the true proportion with 90% confidence will be lower than 0.95%, or in other words a true proportion of 1% is excluded with 90% confidence.

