15.2 Analysis data sets

The total analysis set comprises all subjects who entered the trial. This analysis set includes screening failures. The total population will be used for listing reasons for screening failures and AEs before enrolment.

The safety analysis set is all subject who received at least one dose of IMP. The safety analysis set will be used for all tables and listings.

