Appendix 5**
**Preferred terms for solicited AEs and preferred terms in
aggregated terms**

Trial ID: MT-18

Investigational Medicinal Product: HDM SLIT-tablet

Phase: IV

EudraCT No.: 2020-000446-34

Sponsor: Global Clinical Development
ALK-Abelló A/S
[name]
[contact]

Document Status: Final

Date: 06-Feb-2020

Version: 1.0

Confidential

Property of ALK

May not be used, divulged, published or otherwise disclosed without the written consent of
ALK

Table of Contents

1	Solicited signs/symptoms.....	3
2	Systemic allergic reactions including anaphylactic reactions	4
3	Local swelling or oedema of the mouth and/or throat.....	8
4	Medication errors	9
5	Drug abuse, misuse and overdose	14

1 Solicited signs/symptoms

Preferred terms (PTs) representing the solicited signs/symptoms have been selected (MedDRA 22.1, PTs will be updated to current MedDRA version at the time of reporting). All AEs with these PTs occurring during the 28 days treatment period will be defined as solicited AEs.

Solicited signs/symptoms patient card term	Solicited AE PT
Food taste different	Dysgeusia
Mouth ulcer/sore in the mouth	Mouth ulceration
Swelling of the uvula/back of the mouth	Enlarged uvula Oedema uvula Palatal swelling Palatal oedema Mouth swelling Oedema mouth
Itching of the mouth	Oral pruritus
Itching in the ear	Ear pruritus
Swelling of the lips	Lip swelling Lip oedema
Swelling of the tongue	Swollen tongue Tongue oedema
Tongue pain	Glossodynia
Tongue ulcer/sore on the tongue	Tongue ulceration
Throat irritation/tickle	Throat irritation
Throat swelling	Pharyngeal edema Pharyngeal swelling
Stomach pain	Abdominal pain upper Abdominal pain
Nausea (feel like throwing up)	Nausea
Vomiting	Vomiting
Diarrhea	Diarrhea

2 Systemic allergic reactions including anaphylactic reactions

Cases of possible systemic allergic reaction and/or anaphylaxis are identified by using the following criteria (MedDRA version 22.1, PTs will be updated to current MedDRA version at the time of reporting):

Standardised MedDRA Query (SMQ):

- Anaphylactic reaction, including algorithm:
 - A narrow term from category A;
 - A term from category B – (upper airway/respiratory) AND a term from category C – (angioedema/urticaria/pruritus/flush). Events co-occurring within 24 hours.
 - A term from category D – (cardiovascular/hypotension) AND a term from category B – (upper airway/respiratory) OR a term from category C (angioedema/urticaria/pruritus/flush). Events co-occurring within 24 hours.

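### Solicited symptoms are reported by preferred term only, so a symptom coded to several terms can lack a row for its own frequency and can miss the over-2% tables

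*Combined protocol and SAP*

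**What the plan says.** Section 1.3 states what the solicited data are for: "The secondary endpoints are focused on the characterisation of the frequency of pre-specified particular AEs expected to occur". The diary (section 11.16, Appendix 4) asks about 15 symptoms each day.

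Section 15.8.1 tabulates every AE type in its endpoint table, solicited TEAEs included, by system organ class and PT. For the commoner events it adds: "Most frequent AEs defined as those occurring in more than 2% of subjects will be summarised according to SOC and PT". Two further displays depend on that selection: "Duration of most frequent AEs, as well as time to onset of most frequent AEs, will be summarised according to SOC and PT". No table by diary symptom is planned.

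Appendix 5, section 1 links diary symptoms to PTs. The item on swelling of the uvula or back of the mouth has six: "Enlarged uvula Oedema uvula Palatal swelling Palatal oedema Mouth swelling Oedema mouth". Lip swelling has two: "Lip swelling Lip oedema". Tongue swelling, throat swelling and stomach pain also have two each. The other ten items, among them mouth itch, ear itch and throat irritation, have one each.

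On the denominator, section 15.1 says: "Approximately 250 subjects will be included in the study". Section 15.2 says: "The safety analysis set will be used for all tables and listings".

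**The concern.** The data are collected by symptom but reported by PT. For ten symptoms the two coincide. For the other five, including all four swelling items, the recorded wording and its coding decide which row a case falls in; several of the paired terms differ only in saying swelling or oedema.

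Where coding divides a symptom's cases, three things follow.

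- No planned row gives the number of subjects with that symptom, each counted once.
- The largest PT row falls below that number, unless every affected subject also carries that PT. Adding the rows does not recover it, because one subject can appear in two of them: section 12.3 calls for a new AE form when an event re-appears or changes in severity.
- The symptom can exceed 2% and still be absent from the most-frequent-AE table and from the duration and time-to-onset summaries tied to it.

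When it occurs, the error makes a reaction look rarer than it was. The trial is meant to support an adolescent indication (sections 1.3 and 15.1), and section 1.4 names swelling in the oral cavity as a risk.

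**Working it through.** The plan gives no figure on this point to reproduce, so the check starts from its stated inputs.

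**Inputs.** N of about 250 (section 15.1); cut of more than 2% (section 15.8.1), read as applying per PT; number of PTs per symptom k = 2 or 6 (Appendix 5, section 1).

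**The cut in subjects.** This is the smallest x with x/N > 0.02.
- N = 250: 5/250 = 2.0% does not exceed 2%; 6/250 = 2.4% does. The cut is 6.
- N = 240 to 249: 0.02 × N runs from 4.80 to 4.98, so the cut is 5.

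**Most subjects a symptom can have with no PT selected.** This is k × (x − 1), reached only with no subject in two PTs and every PT one short of the cut.
- N = 250: 2 × 5 = 10 (4.0%); 6 × 5 = 30 (12.0%).
- N = 240 to 249: 2 × 4 = 8; 6 × 4 = 24.

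**How likely a miss is.** The documents give neither symptom rates nor a coding split, so both are assumed and varied. Model: X ~ Binomial(250, p) subjects have the symptom; each is assigned one PT, with counts multinomial with shares w; a miss is X ≥ 6 with every PT count ≤ 5. Results are from 100,000 simulated trials per cell.

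| PTs and assumed split | p = 3% | p = 5% | p = 8% |
|---|---|---|---|
| 2, 50/50 | 44% | 15% | under 1% |
| 2, 70/30 | 32% | 9% | under 1% |
| 2, 90/10 | 9% | 2% | under 1% |
| 6, even | 75% | 88% | 46% |
| 6, 70% in one, 6% in each other | 33% | 11% | under 1% |
| 6, 90% in one, 2% in each other | 9% | 2% | under 1% |

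For reference, the chance that the symptom itself exceeds the cut is 76% at p = 3%, 99% at 5% and essentially 100% at 8%. A one-PT symptom is selected with those probabilities and is never missed in this sense.

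**Sensitivity to overlap.** One PT per subject is the least favourable case for the plan. If 30% of affected subjects receive a second draw from the same shares (also an assumption), the miss at p = 5% falls from 88% to 74% for the even six-way split, and from 15% to 9% for 50/50.

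**The case against.** A reader might infer that swelling frequencies will be understated, with up to 12% of subjects hidden. The documents do not support that.

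- A PT count is correct for its PT. It understates the symptom only if coding divides the cases. All subjects see the same diary wording, which makes an even split between swelling and oedema less plausible for lip, tongue and throat, although the investigator still records the AE term. With 90% in one PT the miss is about 2% at a true 5%.
- The 12.0% needs exactly five subjects in each of six PTs, no overlap and N of at least 250. It is a bound, not an expectation.
- Only selected displays are at risk. Every PT still appears in the full TEAE and solicited-TEAE tables, all AEs are listed (section 15.8), and the duration summary for recurrent TEAEs is by PT with no 2% gate.
- The primary endpoint and the single solicited endpoint in section 2.3 pool across PTs and do not change. No per-symptom endpoint is defined.
- The problem is not specific to swelling, since stomach pain is split too.
- The counting unit of the 2% rule is not stated. PT level is the natural reading, but it is inferred.

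All of this stands. A further objection, that Appendix 5, section 3 already pools swelling terms, stands only in part. Sections 2.4, 12.1.1 and 15.8.1 restrict that event to severe swelling. Its 21 PTs omit 4 of the 12 behind the swelling items (both lip terms, *Enlarged uvula* and *Oedema uvula*), include others such as dysphagia and dysphonia, and give one total, not a figure per symptom. The anaphylaxis query in Appendix 5, section 2 also groups terms, but to find systemic reactions.

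**Conclusion.** The point holds as a conditional reporting gap and not as an established bias. For five of the 15 solicited symptoms the plan has no row that is sure to give the symptom's frequency, although section 1.3 sets out to characterise the frequency of pre-specified events. Whether any frequency is understated depends on a coding split that the documents do not give.

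For two-PT symptoms the exposure is mainly at true rates of about 2 to 5%, and it is negligible by 8%. For the six-PT symptom it is similar if one PT takes 70% of cases, and much larger if coding is spread evenly. These sizes rest on N = 250, a per-PT reading of the 2% rule, the assumed rates and splits, and one PT per affected subject. A cheap improvement is worth making before the data are seen, so that the grouped table does not have to be labelled post hoc.

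**What to change.** In section 15.8.1 add: *Solicited TEAEs will also be summarised by the 15 diary symptoms, grouping PTs as mapped in Appendix 5, section 1, with each subject counted once per symptom and an exact 95% confidence interval. For solicited symptoms, the 2% rule and the duration and time-to-onset summaries that depend on it will be applied to the grouped symptom. For all other AEs the 2% rule applies per PT.* Keep the existing tables by system organ class and PT.

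The last sentence settles the counting unit that section 15.8.1 leaves unstated. The cost is one extra table from an existing map, with no new data. Some swelling frequencies may look higher than in a PT-only report.

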15.8.2 Evaluation of other safety parameters

Vital signs, physical examination assessments, and laboratory assessments will be summarised by visit.

The pulmonary function test parameters (FEV₁, FVC, percentage predicted FEV₁ and percentage predicted FVC) will be summarised by visit.

16 QUALITY ASSURANCE AND CONTROL

16.1 Monitoring

Regular monitoring visits will be performed according to ICH GCP. Data will be evaluated for compliance with the protocol and accuracy in relation to source documents. In accordance with written SOPs, the CRAs will verify that the clinical trial is conducted, and data are generated, documented and reported in compliance with the protocol, GCP and the applicable regulatory requirements.

16.2 Source data and access to source documents

Prior to start of recording of data from subjects, the investigator, with the aid of the CRA, will prepare a source data location agreement to document where the first recording of data is done.

As a minimum requirement, the following data must be source data-verifiable in source documentation other than the eCRF:

- Subject's month³⁴ and year of birth
- Confirmation of participation in the trial (trial ID, subject number, diagnosis)
- Date of informed consent/assent
- Confirmation of subject eligibility (in-/exclusion criteria)
- Concomitant diseases and medication
- Relevant medical history (incl. specific allergy and asthma history and date of diagnosis)
- Relevant previous medication (incl. medication for allergy and asthma)
- Any AEs and SAEs should be described in detail
- Date and number of each trial visit including signature and/or initials of persons conducting the trial visit
- Date and information of any relevant telephone contact with the subject and signature and/or initials of persons conducting or receiving the call
- IMP dispensed/returned

³⁴ For countries where it is allowed

- Subject discontinuation from the trial including reason

Documentation of assessments made during the trial, e.g. FEV₁, SPT and laboratory results must be kept in the subject's medical record, evaluated, signed and dated by an investigator at the trial site. Documentation on thermo-sensitive paper must be copied and signed by the investigator. The copy signed by the investigator should be kept together with the original in the subject's medical record.

The following data could be recorded directly in the eCRF and is then considered to be source data (if acceptable by national legislation and hospital routine):

- Demography and body measurements
- Vital signs
- Physical examination
- Smoking habits

The investigator must give the CRA direct access to examine, analyse and verify any medical records or reports to procedures, source documentation, data records and reports used, referenced or created as part of the conduct of this trial (e.g. relevant hospital or medical records), to confirm consistency with eCRF entries.

The CRA will examine the electronic medical record system and decide on one of the following options for source data verification:

- Option 1
If an audit trail is available, the CRA may choose either to perform source data verification through a direct comparison of the eCRF and the electronic medical record
- Option 2
If no audit trail is available, relevant source data from electronic medical records should be printed out by the investigator or delegate preferably at the day of the monitoring visit. The investigator or delegate must sign and date the printout to confirm that the print and the electronic source data are identical. The CRA must verify the original source data at least once during the trial.

Either option will be agreed with the investigator prior to trial start.

All documents must be stored safely under confidential conditions. On all trial-specific documents, other than the signed consent, the subject will be referred to by the subject ID number. If ALK becomes aware of the identity of a subject, ALK is bound to keep this information confidential and to take immediate actions to delete any information received that identifies the subject.

16.3 Investigator site file – and other trial documentation

The investigator must maintain source documents for each subject in the trial in accordance with local legislation.

The investigator must retain the investigator site file for at least 25 years or in accordance with local legislation.

No trial related documentation may be destroyed by the investigator without prior written agreement with ALK. The investigator agrees to adhere to the document retention procedures by signing the protocol.

Should the investigator choose to transfer the trial documents to another physician or institution, ALK must be notified.

16.4 Protocol compliance

The instructions in the protocol must be followed. If deviations occur, the investigator must inform the CRA, and the implications of the deviation must be reviewed and discussed. Deviations must be documented (or included in eCRF data). In addition, deviations must be accompanied by a description of the deviation, the relevant dates and the action taken. Deviation reports and supporting documentation must be kept in the investigator's file and in the ALK trial master file.

If a deviation that is likely to affect to a significant degree the safety or rights of a subjects or the reliability and robustness of the data generated in the clinical trial (serious breach) has occurred, the investigator should inform the Clinical research organisation (CRO) within 24-hours.

16.5 Audit

ALK may conduct audit(s) of clinical research activities in accordance with internal SOPs to evaluate compliance with GCP and international and local guidelines and regulations.

The investigator must be available during the audit and give the auditors direct and unlimited access to source documentation and data, records and reports used, referenced or created as part of the performance of this trial.

17 ETHICS AND REGULATORY PROCEDURES

17.1 Statement of compliance

This trial must be carried out in compliance with the protocol, which is designed to ensure adherence to the Declaration of Helsinki and the principles of GCP, as described in:

- The Declaration of Helsinki (1964, and its amendments and subsequent clarifications) (**World Medical Association 2013**)
- ICH Harmonised Tripartite Guidelines for GCP, 1996 (**ICH 1996**) including amendments
- EU Directive 2001/20/EC of the European Parliament and of the Council on the Approximation of the Laws, Regulations and Administrative Provisions of the Member States Relating to the Implementation of Good Clinical Practice in the Conduct of Clinical Trials on Medicinal Products for Human Use. 2001 (**2001**)
- European Commission. Commission Directive 2005/28/EC of 8 April 2005 laying down principles and detailed guidelines for Good Clinical Practice as regards investigational medicinal products for human use, as well as the requirements for authorisation of manufacturing or importation of such products. 2005 (**European Commission 2005**)
- FDA regulations relating to GCP and clinical trials, (**FDA 2018**)

- General Data Protection Regulation (GDPR) (Regulation (EU) 2016/679) (The European parliament 2016)

17.2 Disclosure and confidentiality

By signing the protocol, the investigator agrees to keep all information, data and materials whether in oral, written, graphic, electronic or other form provided by ALK or a third party acting on behalf of or at the instruction of ALK in strict confidentiality.

Trial documents provided by ALK (protocol, IB, CRFs and other material) should be stored appropriately to ensure their confidentiality. The information provided by ALK to the investigator may not be disclosed to others except as expressly authorised by this protocol or the clinical trial agreement or with the prior written consent of ALK.

The investigator may disclose confidential information to employees of the investigator, hospital authorities and IECs on a need-to-know basis and only if the aforementioned parties are bound or obligated by provisions of confidentiality no less strict than imposed upon the investigator under this protocol or the clinical trial agreement. Further, the investigator may disclose confidential information set out in the protocol to the extent necessary to obtain informed consent from subjects who wish to participate in the trial.

Any data, results, reports, findings, discoveries and any other information developed or collected during this trial shall be regarded as ALK's confidential information until published.

Financial disclosure from the investigators will be obtained before the trial.

